## **7 STUDY TREATMENTS**

### **7.1 Description of investigational medicinal product(s)**

The IMP (double-blind study treatment: CZP or placebo), will be supplied under the responsibility of the UCB Clinical Supply Unit. The frequency at which IMP will be supplied to each individual center will be adapted to the recruitment capacity of that center and to the expiry date of the IMP and will be managed by the interactive response system (IXRS).

Drug supplies will consist of the following:

Certolizumab pegol is supplied as a sterile, clear, colorless to slightly yellow liquid solution with a pH of approximately 4.7 in 1mL single use glass prefilled syringe (PFS) with a 25G ½ inch thin wall needle for sc injection. Each syringe contains an extractable volume of 1mL at a concentration of 200mg/mL of CZP in 10mM sodium acetate buffer and 125mM sodium chloride as a tonicity agent.

Placebo is supplied in a PFS with a 25G ½ inch thin wall needle, containing an injectable volume of 1mL 0.9% saline for single use.

Due to the difference in presentation and viscosity between CZP and placebo, special precautions will be taken in order to ensure maintained blinding of the study (unblinded/blinded site personnel and monitors).

## 7.2 Treatment(s) to be administered

Treatments to be administered are as described in Section 5.1.

### 7.2.1 Treatment administration

A pharmacy manual will be provided to each site containing instructions regarding drug preparation and dosing. The injection schedule through Week 52 is presented in Figure 7-1. The injection schedule for the SFE Period is presented in Figure 7-2.

At on-site visit days (at Weeks 0, 2, 4, 6, 8, 10, 12, 16, 20, 24, 28, 32, 36, 40, 44, 48, and 50), the double-blind study treatments will be administered sc at the study site. At the Week 0, 2, 4, 6, and 8 visits, the administration must be done by dedicated, unblinded, and adequately trained site personnel. At the Week 10 and 12 visits, the subject will receive training on self-injection and the study treatment will be self-administered under the supervision of the unblinded study personnel. At Weeks 16, 20, 24, 28, 32, 36, 40, 44, 48, and 50, the study treatment administration should preferably be done by the unblinded study personnel, or alternatively by self-injection of the subject under the supervision of the unblinded study personnel. The double-blind study treatment will be self-injected at home at Weeks 14, 18, 22, 26, 30, 34, 38, 42, and 46.

Injections should be administered with a minimum of 10 days between the CZP 200mg Q2W injections.

[figure not shown]
During the SFE Period, CZP will be administered sc by dedicated unblinded study personnel at the study site on Weeks 52, 54, and 56 for subjects completing double-blind treatment in order to maintain the blind. Subjects who complete the Week 52 Visit on placebo treatment will receive loading doses of CZP 400mg at these visits. Subjects who complete the Week 52 Visit on CZP treatment will receive 1 injection of CZP 200mg and 1 injection of placebo at these visits to continue their previous CZP treatment regimen.

Subjects who withdrew from double-blind study treatment and transitioned to open-label CZP treatment do not need to visit the site at Week 54 and Week 56, and should continue their open-label CZP treatment regimen.

For the remainder of the SFE Period, CZP can be administered at the site by dedicated study personnel, or by self-injection of the subject under the supervision of the dedicated study personnel, or subjects may self-administer their study treatment Q2W at home.

**7.2.2 Study AS0006 injection schedule**

**Figure 7-1: Injection schedule through Week 52**

[figure not shown]

○ Placebo  
● CZP

**Loading doses**  
● On site (injection by unblinded site personnel)  
● Self-injection (by subject at home)  
 H Home

CZP=Certolizumab pegol; H=home

**Figure 7-2: Injection schedule for the SFE Period**

○ Placebo  
● CZP

□ Loading doses (on site, to be administered by unblinded site personnel only)  
□ On site (injection preferably by subject; or site personnel, if appr.)  
□ Self-injection (by subject at home)  
H Home

CZP=Certolizumab pegol; FU=follow-up; H=home; SFE=Safety Follow-Up Extension; W=week  
 \* Subjects who complete either double-blind treatment or open-label CZP-treatment and all assessments at Week 52 are eligible to roll-over to the SFE Period.  
 Subjects who complete alternative treatment must finish the study at Week 52 and be scheduled for the final FU visit (8 weeks after the Week 52 Visit).  
 \*\* Subjects rolling over from open-label CZP-treatment to the SFE Period can self-administer their study medication at home from Weeks 2 to 10.  
 \*\*\* Subjects will complete the study assessments at Week 52 according to the protocol and be invited for the final FU visit 8 weeks after Week 52.

---

### **7.3 Packaging**

Certolizumab pegol and placebo are packaged and labeled according to Good Manufacturing Practice (GMP) guidelines and applicable laws or regulations. They are suitably packaged in such a way as to protect the IMP from deterioration during transport and storage.

### **7.4 Labeling**

Clinical drug supplies will be labeled in accordance with the current International Council for Harmonisation (ICH) guidelines on Good Clinical Practice (GCP) and GMP and will include any locally required statements. If necessary, labels will be translated into the local language. Details on Labeling will be provided in the Pharmacy manual.

### **7.5 Handling and storage requirements**

The Investigator (or designee) is responsible for the safe and proper storage of IMP at the site. The IMP stored by the Investigator is to be kept in a secured area with limited access. The IMP containers should be stored at 2 to 8°C and protected from light. Additional information regarding the receipt of the drug and return handling will be specified in the Pharmacy Manual.

Appropriate storage conditions must be ensured by a controlled temperature and by completing a temperature log in accordance with local requirements but at least once per working day with minimum and maximum temperatures reached over the time interval.

In case an out of range temperature is noted, it must be immediately communicated to the Sponsor' designee in accordance with the Pharmacy Manual.

The Investigator (or designee) will instruct the subject to store the IMP following the instructions on the label.

Detailed information on handling and storage of IMP will be given in the Pharmacy Manual.

### **7.6 Drug accountability**

A drug accountability form will be used to record IMP dispensing and return information during the course of the study. Details of any drug lost (due to breakage or wastage), not used, disposed of at the study site, or returned must also be recorded on the appropriate forms. All supplies and pharmacy documentation must be made available throughout the study for UCB (or designee) to review.

Periodically, and/or after completion of the clinical phase of the study, all used (including empty containers) and unused IMP containers must be reconciled and returned to UCB (or designee), preferably in their original packaging. Instructions on how to use and store the IMP will be provided. Investigational medicinal product intended for the study cannot be used for any other purpose than that described in this protocol.

The Investigator (or designee) is responsible for retaining all used, unused, and partially used containers of IMP until returned or destroyed.

The Investigator may assign some of the Investigator's duties for drug accountability at the study site to an appropriate pharmacist/designee.

The Investigator must ensure that the IMP is used only in accordance with the protocol.

All study drug documentation (eg, shipping receipts, drug accountability logs, IXRS randomization materials) must be maintained and accessed by unblinded, trained site personnel only. Designated, unblinded site personnel must be appropriately trained and licensed (per country guidelines) to administer injections. Each site will be required to have a written blinding plan in place signed by the Principal Investigator, which will detail the site's steps for ensuring that the double-blind nature of the study is maintained from Week 0 to Week 52/WD.

### 7.7 Procedures for monitoring subject compliance

Drug accountability must be recorded on the drug accountability form.

If a subject is found to be persistently noncompliant (missing 3 or more doses over any period of 52 weeks), the subject will be withdrawn from the study. A subject will be withdrawn from the study if 3 consecutive doses were missed prior to the primary endpoint assessment. No missing doses are allowed in the first 12 weeks of the study. Doses of IMP that were missed due to a reasonable interfering AE that does not allow administration of an anti-TNF due to safety reasons will not be considered for the evaluation of subject compliance. Evaluation of the reasonability of the AE must be discussed immediately with the Medical Monitor.

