At on-site visit days (at Weeks 0, 2, 4, 6, 8, 10, 12, 16, 20, 24, 28, 32, 36, 40, 44, 48, and 50), the double-blind study treatments will be administered sc at the study site. At the Week 0, 2, 4, 6, and 8 visits, the administration must be done by dedicated, unblinded, and adequately trained site personnel. At the Week 10 and 12 visits, the subject will receive training on self-injection and the study treatment will be self-administered under the supervision of the unblinded study personnel. At Weeks 16, 20, 24, 28, 32, 36, 40, 44, 48, and 50, the study treatment administration should preferably be done by the unblinded study personnel, or alternatively by self-injection of the subject under the supervision of the unblinded study personnel. The double-blind study treatment will be self-injected at home at Weeks 14, 18, 22, 26, 30, 34, 38, 42, and 46.

Concomitant medications permitted during the study should remain stable for at least 4 weeks prior to the Weeks 12, 24, and 52/WD assessments.

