### 6.3 Withdrawal criteria

Subjects are free to withdraw from the study at any time, without prejudice to their continued care.

Subjects should be withdrawn from the study if any of the following events occur:

1. Subject develops an illness that would interfere with his/her continued participation.
2. Subject is noncompliant with the study procedures or medications in the opinion of the Investigator.
3. Subject withdraws his/her consent.
4. There is confirmation of a pregnancy during the study, as evidenced by a positive pregnancy test (see [Section 12.1.6](#) for more information regarding pregnancies).
5. The Sponsor or a regulatory agency requests withdrawal of the subject.
6. Subject's subsequent TB test was confirmed positive or any further evidence is suggestive of potential TB infection (eg, exposure). Refer to [Section 12.6.3](#) for further details and instructions.

Subjects should be withdrawn from the study-treatment if,

7. The Investigator decides to initiate an alternative treatment due to an unsatisfactory response to the study treatment, or
8. Subjects take any of the prohibited medications in [Table 7–1](#) and [Section 7.8.2](#)

If a subject is withdrawn from the double-blind study treatment, the Investigator should encourage the subject to continue participation in the study in accordance with the appropriate alternative schedule of study assessments ([Table 5–2](#) or [Table 5–3](#)). The treatment that the subject receives following withdrawal of study medication is at the discretion of the Investigator,

with open-label CZP available as a treatment option according to the local requirement mandated in the region. UCB will provide this medication free of charge. Alternatively, the Investigator may treat the subject with other treatments (including biologics) as deemed appropriate by local regulations. If the Investigator chooses to withdraw subjects on the other therapy, the local guidelines on initiation and monitoring of the particular treatment should be followed.

Investigators should contact the Medical Monitor, whenever possible, to discuss the withdrawal of a subject from the double-blind study treatment in advance. The reason for discontinuation of the double-blind study treatment must be recorded in the case report form (CRF) as appropriate.

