Although the subject may be withdrawn from the double-blind study treatment at any time, every effort should be made to retain the subject in the study and encourage compliance of the subject with the scheduled study visits. For subjects who fail to return to study visit(s) or are considered lost to follow up, the Investigator should specifically communicate (at least 1 phone call and 1 written message to the subject), and document his/her effort (date and summary of the phone call and copy of the written message in the source documents). In case the attempts to direct contact the subject fail, the Investigator is encouraged to gain information about the wellbeing of the subject at the end of the regular visit schedule (Week 52/WD) from other sources in compliance with local regulations. All results of observations and communication with the subject, including and not limited to the relevant information on his/her wellbeing, must be recorded in the source documents.

If a subject is withdrawn from the study, the narrative description of the reason(s) for removing the subject must be recorded in the source documents. The CRF must document the primary reason for withdrawal.

Subjects withdrawn from the study will not be replaced.

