### **14.3 Planned efficacy analyses**

The primary efficacy variable measurement for this study is based on ASDAS-MI response at Week 52. The associated primary outcome of the study will be defined as a composite endpoint that is achieved if a subject fulfills the following 2 components:

1. Remain in the study and on the double-blind study treatment through 52 weeks
2. Achieve an ASDAS-MI response at 52 weeks

For simplicity, this primary efficacy variable will be referred to as ASDAS-MI response at Week 52. However, the composite definition as described above will apply when this endpoint is analyzed. The primary analysis for this endpoint will be based on logistic regression. The odds ratio of the ASDAS-MI responder rates at Week 52 will be estimated and tested between treatment groups using a logistic regression model with factors of treatment group, region, and MRI/CRP classification (MRI+/CRP+; MRI+/CRP-; MRI-/CRP+). If the logistic regression

model is unable to converge, then the MRI/CRP classification variable may be dropped from the model to facilitate convergence. The study design is likely to result in some sites with a small number of enrolled subjects. The use of region as a stratification variable and as a factor in the model is intended to combine study centers in similar geographic regions. The geographic regions to be used will be defined in the IXRS and in the SAP. Given the composite endpoint definition described above, there will be no missing data for the primary endpoint, as subjects that discontinue the double-blind study treatment prior to Week 52 or who do not have an ASDAS-MI status at Week 52 are considered nonresponders to the double-blind study treatment.

As described in Section 6.3, subjects who discontinue the double-blind study treatment will not necessarily be withdrawn from the study. In an attempt to minimize missing data, efforts will be made to continue to collect safety and efficacy data on these subjects through study completion. Sensitivity analyses will be performed to evaluate the impact of missing data on the analysis of the primary efficacy variable (see Section 14.8).

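### The missed-dose rule takes subjects out of the study, not only off blinded treatment, and so creates avoidable missing Week 52 data that the plan says it wants to collect

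*Protocol*

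**What the plan says.** Section 7.7 of the protocol contains three statements about missed doses.

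- For persistent noncompliance: "missing 3 or more doses over any period of 52 weeks), the subject will be withdrawn from the study".
- For consecutive misses: "A subject will be withdrawn from the study if 3 consecutive doses were missed prior to the primary endpoint assessment".
- No dose may be missed in the first 12 weeks. No consequence is attached to this.

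One exception is given: "Doses of IMP that were missed due to a reasonable interfering AE" that makes anti-TNF dosing unsafe are not counted.

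Section 6.3 has two lists. Criteria 1 to 6 lead to withdrawal from the study. Criteria 7 and 8 (a change to alternative treatment for unsatisfactory response, and use of prohibited medication) lead to withdrawal from study treatment only. Criterion 2, in the first list, reads "Subject is noncompliant with the study procedures or medications in the opinion of the Investigator".

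Other text points the opposite way. Section 6.3 says that after withdrawal from blinded treatment "every effort should be made to retain the subject in the study and encourage compliance of the subject with the scheduled study visits". Section 14.3 says, of subjects who stop blinded treatment, that "efforts will be made to continue to collect safety and efficacy data on these subjects through study completion", and gives the purpose as keeping missing data to a minimum. Section 14.8 plans a sensitivity analysis that takes the Week 52 outcome whether or not the subject is still on randomized treatment, and counts anyone without one as a non-responder.

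**The concern.** Section 6.3 itself separates leaving treatment from leaving the study, and both it and Section 7.7 put missed doses on the study side. The result is uneven. A subject who takes a prohibited medicine comes off treatment but can be followed to Week 52. A subject who misses three injections is removed from the study.

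Three things are at stake.

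- **Observed-data sensitivity analyses (Section 14.8).** These exist to use actual Week 52 outcomes after treatment has stopped. A subject removed for missed doses cannot supply one. For a binary endpoint that subject is scored a non-responder, whatever the true disease state.
- **Anterior uveitis through Week 52 (Sections 14.2, 14.4 and 14.8).** This is the eleventh and last test in the fixed sequence. A subject with no new event at the post-Baseline visits is classed as not having had a flare, and a value is treated as missing only if there was no post-Baseline uveitis assessment at all. A subject removed early can therefore count as flare-free on truncated follow-up in the main analysis.
- **Safety follow-up.** It ends with the withdrawal and follow-up visits instead of running to Week 52.

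**Working it through.** **Dosing occasions.** Section 5.1.1 lists on-site dosing "at Weeks 0, 2, 4, 6, 8, 10, 12, 16, 20, 24, 28, 32, 36, 40, 44, 48, and 50", which is 17 occasions, and doses "self-injected at home at Weeks 14, 18, 22, 26, 30, 34, 38, 42, and 46", which is 9. The total is 17 + 9 = 26, every two weeks from Week 0 to Week 50. Three missed doses are 3/26 = 11.5%, so a subject who took 23/26 = 88.5% of doses meets the rule.

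**The plan's own power figure.** Section 14.10 states 95% power for 40% versus 20%, with 150 per group and two-sided alpha 0.05. By the normal approximation:

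- pooled standard error = √(2 × 0.30 × 0.70 / 150) = 0.0529
- unpooled standard error = √((0.40 × 0.60 + 0.20 × 0.80) / 150) = 0.0516
- power = Φ((0.20 − 1.96 × 0.0529) / 0.0516) = 96.9%

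With a continuity correction it is 95.9%. The stated figure is reproduced and is not in dispute.

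**Effect on the primary endpoint.** Section 14.3 requires a responder to stay in the study and on blinded treatment through Week 52.

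- Removed from the study: non-responder.
- Taken off blinded treatment but followed to Week 52: non-responder.

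The two are scored alike, so the difference between study withdrawal and treatment withdrawal changes neither the composite response rates nor the power.

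**Effect on other analyses.**

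- Main analysis of the continuous secondary variables (Section 14.4): data after treatment discontinuation are imputed anyway, so little changes.
- Multiple imputation, observed-case and tipping-point sensitivity analyses (Section 14.8): the first treats post-discontinuation data as missing, the second excludes them, and the third varies assumptions about subjects who discontinued. Little changes.
- Analysis including observed data at Week 52: the outcome is lost.
- Anterior uveitis and safety: follow-up is cut short.

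**How many subjects.** The protocol gives no miss rate. Assume that misses are independent, occur at rate *m* per dose and are not excused for an adverse event. Then

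P(3 or more of 26) = 1 − Σ C(26, k) mᵏ (1 − m)²⁶⁻ᵏ, summed over k = 0, 1, 2.

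- m = 1%: 0.2%, about 1 of 300
- m = 2%: 1.5%, about 4 of 300
- m = 3%: 4.2%, about 13 of 300
- m = 5%: 13.9%, about 42 of 300

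**Overlap within Section 7.7.** Three consecutive misses before the Week 52 assessment already meet the condition of three or more in 52 weeks and carry the same consequence, so that statement adds nothing. The first-12-weeks statement does not tell a site what follows a single early miss.

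**The case against.** The strongest reply is that Section 6.3 separates the two kinds of withdrawal on purpose. Its text on alternative schedules applies to subjects withdrawn from blinded treatment, and Section 14.3 says only that such subjects will not necessarily leave the study. Section 14.8 openly expects some missing Week 52 data and says how to handle them. Most analyses are untouched, 17 of the 26 doses are given on site, and misses excused for an adverse event do not count. A subject who is withdrawn still has the full Week 52/WD visit assessments and a follow-up visit 8 weeks later, and adverse events are usually followed for 70 days after the last treatment. The uveitis sensitivity analyses adjust for exposure time.

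Much of this stands, and it limits the weight of the point. It does not remove the tension. An assessment made at early withdrawal is not a Week 52 outcome, and the exposure-adjusted uveitis analysis is not the confirmatory test. Expecting some missing data is also not a reason to create more by rule.

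A reader might infer that the rule costs power. If 10% of each arm were removed, 40% and 20% would become 36% and 18%, and power would be 94.3%, below the stated 95%. The documents do not support that as an effect of study withdrawal. Those subjects are composite non-responders once off blinded treatment, so keeping them in the study would recover none of the loss. The planning rates carry the composite endpoint's name, so they may already allow for subjects who leave treatment. The 10% is not in the protocol.

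**Conclusion.** The point holds as a conflict between sections. Section 7.7 and Section 6.3 criterion 2 end study participation for missed doses. The retention text in Section 6.3 and the analysis aims in Sections 14.3 and 14.8 call for Week 52 outcomes from subjects who stop blinded treatment. The damage is confined to the observed-data sensitivity analyses, the uveitis count and safety follow-up to Week 52. The primary result and its power are unaffected, provided that a breach of the rule still ends blinded treatment.

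The size cannot be fixed from the documents. The range of about 1 to 42 of 300 subjects rests on an assumed independent, non-excused miss rate of 1% to 5% per dose. If misses cluster within subjects, the share would differ.

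**What to change.** Reconcile Section 7.7, Section 6.3 (criterion 2 and the retention paragraph), Section 14.3 and Section 14.8. Whatever missed-dose rule the sponsor keeps, state its consequence for treatment separately from its consequence for study participation. Say that a subject who breaches it is still invited to the Week 52 efficacy, extra-articular and safety assessments, unless consent is withdrawn or another study-withdrawal criterion applies. The criteria on illness, pregnancy, sponsor or regulator request, and tuberculosis stay as they are.

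Referring these subjects to Tables 5-2 and 5-3 would not be enough. Both schedules presuppose that a new treatment is started, and the assessments listed in Section 8.9 for other treatment do not include the extra-articular ones. The Week 52 invitation should therefore be written out.

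The sponsor should also reconcile the three overlapping statements in Section 7.7, including the missing consequence for a dose missed in the first 12 weeks. Which dosing rule to keep is for the sponsor to decide.

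The cost is an amendment to the wording and a few additional visits.
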